Congenital hyperinsulinism (HI) is a disorder of β -cell dysregulation in the pancreas that results in severe hypoglycemia. Frequently, pancreatectomy is necessary to control hypoglycemia. After near-total pancreatectomy, diabetes is common with 91% of the individuals requiring insulin before puberty. Current treatment involving insulin administration offers inadequate blood glucose (BG) control in these individuals. We propose a novel approach to better treat these individuals through use of a bihormonal “bionic pancreas” to replace both hormones, insulin and glucagon, through an automated glycemic management system.

In collaboration with the Bionic Pancreas Project, we propose a pilot study to evaluate the efficacy and safety of the bionic pancreas in individuals with HI and post-pancreatectomy diabetes. Potential subjects will be recruited from The CHOP Congenital Hyperinsulinism Center. Eligibility entails six to 30 years in age, an HI diagnosis, and post-pancreatectomy diabetes managed by subcutaneous insulin pump. Subjects will be studied during two research inpatient admissions at the CHOP HI Center. During one admission - standard care - subjects will continue their home insulin regimen via their insulin pump; during the other admission – bihormonal bionic pancreas admission - subjects will receive insulin and glucagon via the bihormonal bionic pancreas. Glycemic control will be evaluated through a continuous glucose monitoring system. Mean glucose and episodes of hypoglycemia will be compared during the two admissions. Data generated from this pilot study will be used to plan a larger study.

PROTOCOL SYNOPSIS

| | |
|------------------------------------|---|
| Study Title | Bihormonal Bionic Pancreas for the Treatment of Diabetes Post-Pancreatectomy in Individuals with Congenital Hyperinsulinism – A Pilot Study |
| Funder | Zealand Pharma A/S |
| Sponsor (IDE holder)/Funder | [name] (Dept of Biomedical Engineering, Boston University) |
| Clinical Phase | Pilot Study |
| Study Rationale | 
The management of diabetes following pancreatectomy for HI generally consists of the same approaches that are used for individuals with type 1 diabetes (T1D). However, there are significant differences in individuals with HI and post-pancreatectomy diabetes that increases the risk of hypoglycemia in these individuals and prevent achieving tight glycemic control. Individuals with HI have glucagon deficiency and unlike T1D, individuals with HI and post-pancreatectomy diabetes have residual dysregulated insulin secretion that results in marked hypo- and hyper-glycemia. Furthermore, pancreatic insufficiency can result in disturbances in nutrient absorption and fluctuations in glucose concentrations.
 
Current treatment approaches with intermittent subcutaneous insulin administration or insulin pump therapy offer inadequate glycemic control in these individuals. We propose a novel approach to the management of these individuals with the bihormonal bionic pancreas to replace both hormones, insulin and glucagon, through an automated glycemic management system.
 |
| Study Objective(s) | 
Primary
 
 To determine if the bihormonal bionic pancreas improves glycemic control in individuals with HI who develop diabetes post-pancreatectomy. 
Secondary
 
 To evaluate the safety of the bihormonal bionic pancreas in individuals with HI who develop diabetes post-pancreatectomy. |
| Test Article(s) | The Bionic-Pancreas Glycemic-Control System has been shown to improve glycemic control and to reduce the frequency of hypoglycemia in children and adults with T1D. Insulin and glucagon are administered by a fully automated, bihormonal, bionic pancreas with the use of control algorithms that adapt to changes in insulin/glucagon requirements. The device consists of an iPhone®, which runs the control algorithm, and a Dexcom® continuous glucose monitor system (CGMS) connected by a custom software |

| | |
|---------------------------|---|
| | interface. Insulin and glucagon are administered subcutaneously by a Tandem® t:slim™ infusion pump, which are controlled wirelessly by the iPhone®. In adults and children with T1D, the combination of insulin and glucagon has been shown to improve glycemic control and reduce the occurrence of hypoglycemia. |
| Study Design | This will be an open-label, pilot clinical trial to assess efficacy and safety of the bihormonal bionic pancreas in children and adults with HI who have developed post-pancreatectomy diabetes. Subjects will be studied during two research inpatient admissions at the CHOP HI Center. The order of the interventions will be randomized. |
| Subject Population | 
Abbreviated Inclusion Criteria
 
 1. Individuals 6 years to 30 years of age. 2. Diagnosis of hyperinsulinism. 3. Previous pancreatectomy. 4. Diagnosis of diabetes. 5. Treatment with subcutaneous insulin by pump at the time of recruitment. 
Abbreviated Exclusion Criteria
 
 1. Evidence of a medical condition that might alter results or compromise the interpretation of results, including active infection, kidney failure, severe liver dysfunction, severe respiratory or cardiac failure. 2. Evidence of severe hematologic abnormality including severe anemia and/or thrombocytopenia. |
| Number of Subjects | 12 subjects enrolled to produce 10 evaluable subjects |
| Study Duration | Each subject's participation will last approximately 8 days (screening visit and two, 4-day inpatient admissions). The entire study is expected to last one year. |
| Study Phases | 
 • Screening: medical records will be reviewed to determine eligibility. Medical history, physical examination, CBC, CMP, and HbA1c will be obtained during this visit after informed consent. • The order of admissions will be determined using a randomized, cross-over design and will occur at least 1 week apart. • Standard Care Admission: A 4-day inpatient admission in which subjects will continue their home insulin regimen. The first day will be a run-in period. The last 3 days involve collection of plasma glucose data for analysis (CGMS and fingerstick). • Bihormonal Bionic Pancreas Admission: A 4-day inpatient admission in which subjects will wear the bihormonal pancreas. |

| | |
|--|---|
| | 
The bihormonal pancreas will be placed upon admission and there will be 1 day of run-in followed by 3 days of data collection for comparison with the data obtained from the standard of care during the control admission. Following this, the patient will transition back to their home regimen and discharged home.
 |
| Efficacy Evaluations | 
The co-primary efficacy evaluations are (1) mean glucose concentration as measured by the CGMS during the last 3 days of the Standard Care Admission and the last three days of the Bihormonal Bionic Pancreas Admission, and (2) the mean proportion of time that the CGMS-measured glucose concentration was less than 60 mg/dL during the same periods.
 
Secondary efficacy evaluations include the proportion of time that CGMS-measured glucose concentrations are in clinically relevant ranges (< 70 mg/dL, 70-180 mg/dL, >180 mg/dL), the mean glucose concentration measured by fingerstick, the proportion of glucose concentrations measured by scheduled fingersticks that were below 60 mg/dL, and the number of interventions required for hypoglycemia per day.
 |
| Safety Evaluations | 
Safety variables will be assessed by comparison of frequency of serious adverse events (SAEs) during the two study periods.
 |
| Statistical and Analytic Plan | 
This is a pilot study to generate data to assess feasibility of study design/procedures and for formal sample size estimation for a larger study of the efficacy of the bihormonal bionic pancreas in children and adults with hyperinsulinism and post-pancreatectomy diabetes. The sample size for this pilot study may be too small to detect statistical significance, however, we offer the following plan for analysis of the outcomes for this study.
 
Descriptive statistics will be used to characterize demographic, baseline, and outcome measures in subjects. Mean CGMS-measured glucose concentration (calculated as the mean of all CGMS-measured concentrations [measured every 5 min] over the study period) and the mean proportion of time when the CGMS-measured glucose concentration was < 60 mg/dL during the last 3 days on the bionic pancreas will be compared to the same outcomes during the standard care period by paired-sample Student's t-test (or Wilcoxon signed rank test if data is not normally distributed) to determine if the intervention conferred an improvement in glycemic control. Secondary outcomes will be analyzed with univariate analysis.
 |
| Data and Safety Monitoring Plan | 
The Principle Investigator (PI) will be ultimately responsible for data quality management and ongoing assessment of safety. Safety variables will be assessed by comparison of frequency of serious adverse events (SAEs) during the two study periods.
 |

Table 1: Schedule of Study Procedures

| Study Phase ^A | Screening | Standard Care Admission | | | | Bihormonal Bionic Pancreas Admission | | | |
|---|-----------|-------------------------|----------------|----------------|-----|--------------------------------------|----------------|----------------|-----|
| | | S.1 | C.0 | C.1 | C.2 | C.3 | E.0 | E.1 | E.2 |
| Visit ID | X | | | | | | | | |
| Informed consent/assent | X | | | | | | | | |
| Review inclusion/exclusion criteria | X | | | | | | | | |
| Demographic/medical history | X | | | | | | | | |
| Physical examination | X | | | | X | | | | X |
| Vital Signs: Ht, Wt, Temp, BP, HR, RR | X | X | X ^D | X ^D | X | X | X ^D | X ^D | X |
| Pregnancy test ^B | X | | | | | | | | |
| Safety laboratory tests | X | | | | | | | | |
| Insulin administered per home regimen | | X | | | | | | | |
| Insulin/Glucagon administration via bionic pancreas | | | | | | | X | | |
| Standardized diabetic meals | | | | | | X | | | |
| BG check by fingerstick ^C | | | | | | X | | | |
| BG monitoring by CGMS | | | | | | X | | | |
| BG telemetric monitoring | | | | | | X | | | |
| Prior/Concomitant Medications | | | | | | X | | | |
| Adverse Event Assessment | | | | | | X | | | |

^A Order of admissions will be determined using a randomized, crossover design.

^B Pregnancy test will be completed for females 11 years of age or older.

^C BG will be checked by fingerstick before each meal, at bedtime, and at least once overnight; episodes of hypoglycaemia will be treated as per standard clinical practice with 15 grams of simple carbohydrates and/or glucagon, if necessary.

^D Vital signs will be measured twice daily on these days. Height will only be measured on Study ID Days S.1, C.0, and E.0. Weight will be measured on Study ID days S.1, C.0, E.0, and at discharge from each admission.

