3.1.1 Screening Phase

Potential subjects will be screened using the protocol inclusion and exclusion criteria. Individuals with HI and post-pancreatectomy diabetes will be recruited from the CHOP Congenital Hyperinsulinism Center.

Parental/guardian permission (informed consent) and, if applicable, child assent, will be obtained prior to any study related procedures being performed.

Medical records will be reviewed to determine eligibility. Medical history, physical examination, CBC, CMP, and hemoglobin A1c will be obtained during this visit after informed consent. Blood samples will be drawn to confirm eligibility based on clinical laboratory parameters. Females ≥ 11 years of age will have a urine pregnancy test.

The order of admissions will be determined based upon a randomized, crossover design with at least one week between admissions.

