3.4.1 Inclusion Criteria

- 1) Males or females age 6 to 30 years.
 - 2) Diagnosis of hyperinsulinism.
 - 3) Previous pancreatectomy.
 - 4) Diabetes confirmed by one or more of the following:
 - a) Glycosylated A1c > 6.4%.
 - b) Fasting glucose > 125 mg/dL.
 - c) 2-hour post-prandial glucose > 200 mg/dL.
 - d) Random glucose > 200 mg/dL with symptomatic hyperglycemia.
 - 5) On insulin therapy with a regimen of at least 11 units/day.
 - 6) Treatment with subcutaneous insulin by pump at the time of recruitment.
 - 7) Prescription medication regimen stable for > 1 month (except for medications that will not affect the safety of the study and are not expected to affect any outcome of the study,
-

in the judgment of the site PI).

- 8) Females \geq 11 years of age must have a negative urine/serum pregnancy test and must use an acceptable method of contraception, including abstinence, a barrier method (diaphragm or condom), Depo-Provera, or an oral contraceptive, for the duration of the study.
- 9) Parental/guardian permission (informed consent) and if appropriate, child assent.

No subjects will be excluded based on gender or race. The requirement that subjects manage their diabetes using subcutaneous insulin infusion pump therapy is imposed because multiple daily injection therapy involves the use of medium-acting or long-acting basal insulin that would require an extended washout period.

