3.4.2 Exclusion Criteria

- 1) Unable to provide informed consent (e.g. impaired cognition or judgment).
 - 2) Evidence of a medical condition that might alter results or compromise the interpretation of results, including active infection, kidney failure, severe liver dysfunction, severe respiratory or cardiac failure.
 - 3) Evidence of severe hematologic abnormality including severe anemia and/or thrombocytopenia.
 - 4) Electrically powered implants (e.g. cochlear implants, neurostimulators) that might be susceptible to radio frequency interference.
 - 5) Unable to completely avoid acetaminophen for duration of study.
 - 6) History of adverse reaction to glucagon (including allergy) besides nausea and vomiting.
 - 7) Established history of allergy or severe reaction to adhesive or tape that must be used in the study.
 - 8) Use oral (e.g. thiazolidinediones, biguanides, sulfonylureas, glitinides, DPP-4 inhibitors, SGLT-2 inhibitors) anti-diabetic medications.
 - 9) Any investigational drug use within 30 days prior to enrollment.
 - 10) Pregnant or lactating females.
 - 11) History of more than one episode of DKA and/or severe hypoglycemia within the six months prior to study enrollment.
 - 12) Current history of sub-optimally treated nausea and/or vomiting.
 - 13) Parents/guardians or subjects who, in the opinion of the Investigator, may be non-compliant with study schedules or procedures.
-

- 14) Current and sustained use of insulin formulation (delivered via pump) not approved/advised to be used in the Tandem t:slim pump.

Subjects that do not meet all the enrollment criteria may not be enrolled. Any violations of these criteria must be reported in accordance with IRB Policies and Procedures.

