4.3 Experimental Procedures and Data Collection

4.3.1 Screening Visit

- After informed consent is obtained, all subjects will have a screening visit to confirm eligibility.
 - The subject will be interviewed and the case report form will be completed by study staff to establish whether the subject is eligible to continue with the screening according to inclusion/exclusion criteria, in the event the medical record review provided outdated data.
 - Demographic/medical history data to be recorded:
 - Age
 - Sex
 - Race and ethnicity
-

- Date of HI diagnosis
- Date of pancreatectomy and percentage removed
- Date of diabetes diagnosis/insulin initiation
- Medical, surgical, and social history, allergies, and review of systems relevant to inclusion and exclusion criteria
- Medications (prescription and non-prescription)
- Duration of insulin pump use
- Type of insulin used in pump
- Average total daily dose of insulin in the last 30 days (from pump history, as available – for comparison with insulin dosing during the standard care and bionic pancreas arms of the study)
- Usage of CGMS, if any (type of CGMS, days per month worn, usage of data, whether insulin is dosed based on CGMS alone, alarm settings)
- Physical examination
- Vital Signs: height, weight, temperature, blood pressure, heart rate, respiratory rate
- Pregnancy test (for female subjects 11 years and older)
- Safety laboratory tests: CBC, CMP, hemoglobin A1c
- Once all the laboratory results have been returned, a study physician will review the case report form to determine subject eligibility to continue in the study. If subjects are not eligible to continue in the study, the results of abnormal tests will be reported to the subjects.
- Subjects who have been screened and are eligible can participate without having to be rescreened for a period of one year. The study staff should obtain verbal confirmation that there have been no health events that would make them ineligible if the interval between screening and participation is longer than 3 months.
- Upon confirmation of eligibility and participant’s willingness to continue, subjects will be assigned to an order of admissions based upon a randomized, crossover design. There will be a minimum of 1 week time between admissions.
- Pediatric subjects will be required to have a parent or guardian accompanying them during the inpatient admissions.

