5.1.4.2 Pregnancy Testing

A urine pregnancy test will be performed for female subjects ≥ 11 years of age and girls <11 years who are physically capable of becoming pregnant.

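### The only scheduled pregnancy test is at screening, which may precede bionic pancreas start by up to about a year, and sections disagree on whether capable girls under 11 are tested

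*Combined protocol and SAP*

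**What the plan says.** Section 3.4.2, item 10, excludes "Pregnant or lactating females", with no age limit. Section 3.4.1, item 1, admits "Males or females age 6 to 30 years", so girls under 11 can enrol.

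**When the test is done.** Table 1 has one mark for the pregnancy test, in the screening column. Sections 3.1.1 and 4.3.1 also place it at screening. The Day 0 lists in 4.4.1 and 4.5.1 include medical history and medications but no pregnancy test.

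**How long screening lasts.** Section 4.3.1 states: "Subjects who have been screened and are eligible can participate without having to be rescreened for a period of one year". If more than 3 months pass, staff should obtain verbal confirmation that no disqualifying health event has occurred. The two admissions must be at least one week apart; no maximum is given.

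**Who is tested.** Table 1 footnote B: "Pregnancy test will be completed for females 11 years of age or older". Sections 3.1.1 and 4.3.1 give the same age limit (for example "Pregnancy test (for female subjects 11 years and older"). Inclusion 8 requires a negative test and acceptable contraception throughout the study from the same age. Section 5.1.4.2 is broader: "female subjects ≥ 11 years of age and girls <11 years who are physically capable of becoming pregnant".

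**The concern.** An exclusion meant to keep pregnant subjects away from an investigational device should be verified close to the time the device is started. Here the only objective check can be many months old by then. A subject whom the protocol intends to exclude could receive automated insulin and glucagon because nobody, including her, knew that she was pregnant.

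The age rule is a second, separate problem. Staff working from the schedule would not test a capable girl under 11; staff working from 5.1.4.2 would. If she is tested, the contraception requirement in inclusion 8 still does not reach her.

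**Working it through.** The plan gives no figure to reproduce. The check is a comparison of sections and one interval.

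**Interval from pregnancy test to device start**

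Inputs: screening validity of 1 year, taken as 365 days (4.3.1); discharge on the fourth day of admission, that is 3 days after Day 0 (4.4.3); minimum gap of 7 days (4.3.1). Assumption: the one-year clause refers to the start of the first admission.

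- Bionic pancreas first: device start up to 365 days after the test.
- Standard care first, beginning on day 365: 365 + 3 + 7 = 375 days at the minimum gap. No maximum gap is stated, so the text does not cap this interval.
- If the clause is instead read to cover both admissions, the ceiling is 365 days in either order.

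The synopsis expects the entire study to last one year, so intervals of this length would be extreme.

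**What stands between the test and the device**

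| Safeguard | Where | When | Detects an unrecognised pregnancy? |
|---|---|---|---|
| Pregnancy test | Table 1, 3.1.1, 4.3.1 | Screening | Only if present at screening |
| Last menstrual period | 5.1.1 | Screening | No, if it begins later |
| Contraception, females 11 or older | 3.4.1, item 8 | Throughout study | No; lowers the chance, depends on adherence |
| Verbal check of health events | 4.3.1 | Only after more than 3 months | No; self-report |
| Medical history | 4.4.1, 4.5.1 | Day 0 of each admission | Not reliably; self-report |

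The Day 0 history applies whatever the interval, so a check does exist before 3 months as well as after. None of the later safeguards is a test.

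**Age rule**

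| Place | Population named |
|---|---|
| Table 1 footnote B | Females 11 or older |
| 3.1.1 | Females 11 or older |
| 3.4.1, item 8 | Females 11 or older (negative test and contraception) |
| 4.3.1 | Females 11 or older |
| 5.1.4.2 | Females 11 or older, plus capable girls under 11 |

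Four places give the narrower rule and one the broader. The two issues can meet: within the one-year validity, a girl screened at 10 may be 11 at admission. The documents do not say at which date age is counted for this purpose.

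**The case against.** The strongest defence is that the plan has several layers. Females 11 or older must use contraception, history is taken at each admission, a verbal check follows a long delay, and the investigator may withdraw a subject for safety (4.12). A positive test would exclude a girl of any age, because exclusion 10 has no age limit. Section 5.1.4.2 is the section dedicated to pregnancy testing and already covers capable girls under 11; the other sections do not say that younger girls must go untested. Table 1 is also not exhaustive: it marks medical history at screening only, although the Day 0 lists require it.

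Much of this stands. It narrows the gap to an unrecognised pregnancy arising after screening, and it makes the age issue an inconsistency rather than an omission. It does not close the gap. The incompleteness of Table 1 does not help either, because the itemised list in 4.5.1 also has no test.

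A reader might infer more than the documents support:

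- *That a pregnant subject would be eligible.* She would not; exclusion 10 still applies. The defect is possible non-detection.
- *That a pregnancy starting between admissions would confound the paired comparison.* The documents say nothing about the effect of pregnancy on insulin requirement or about how often this might happen, so that claim has no basis here.
- *That both admissions need a test.* In the standard care admission subjects stay on their own pump and home regimen, so a test at C.0 would not address exposure to the device.

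**Conclusion.** The point holds as a matter of eligibility verification and internal consistency. A subject can be handled exactly as written and still start the bionic pancreas with exclusion 10 last tested up to about a year earlier: 365 days, or about 375 with standard care first, under the stated reading of the one-year clause. That is a ceiling, not an expected interval.

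The timing gap concerns females from 11 to 30, and any younger capable girl tested under 5.1.4.2. The age inconsistency concerns only capable girls aged 6 to 10. The documents do not say how many of the approximately 12 subjects will be female or give a pregnancy rate, so no probability can be attached. Nothing here changes the sample size or the analysis.

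**What to change.** Add a urine pregnancy test at E.0 in Table 1 and in 4.5.1, with a negative result confirmed before the bionic pancreas is started. Reconcile Table 1 footnote B, 3.1.1, inclusion 8, 4.3.1 and 5.1.4.2 so that one population rule for testing applies throughout, and state whether the contraception requirement in inclusion 8 follows the same population.

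The cost is one urine test per female in the testing population, at an admission already planned, plus wording changes in five places. The downside is an occasional late exclusion. If it came after a completed standard care admission, that pair would be lost, because 6.5 analyses only subjects who complete both periods. The enrolment allowance for all losses is 12 − 10 = 2 subjects.
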